9. STUDY TIMELINES

- *Describe the duration of an individuals participation in the study*
- *Describe the duration anticipated to enroll all study subjects*
- *The estimated date of study completion*

Care partners will participate in the study remotely for a total of 3 months.

We anticipate enrollment to last approximately 1 year. The estimated date of study completion is July 2025.

10. ENDPOINTS

- *Describe the primary and secondary study endpoints*
- *Describe any primary or secondary safety endpoints*

We define the feasibility of conducting a full-scale effectiveness trial as:

- ≥40% of eligible care partners will be consented;
- Attrition rate will be ≤30% at Time Point 3 (care partner burden at 3 months);
- ≥80% of care partners will successfully receive the text message after enrollment (to be verified at the 1-week call with the RA);
- ≥90% of care partners will receive all follow-up text messages (1, 2, and 3 weeks);

- v. $\geq 60\%$ of care partners will access WeCareToFeedDysphagia (defined as reaching the home page); and
- vi. $\geq 45\%$ of care partners will engage (defined as viewing ≥ 2 pages) with WeCareToFeedDysphagia.

We will not proceed with the full-scale RCT to determine the effectiveness of WeCareToFeedDysphagia to reduce care partner burden if we do not meet at least 3 out of the 6 criteria outlined above.

11. RESEARCH PROCEDURES

- *Include a detailed description of all procedures to be performed on the research subject and the schedule for each procedure.*
- *Include any screening procedures for eligibility and/or baseline diagnostic tests*
- *Include procedures being performed to monitor subjects for safety or minimize risks*
- *Include information about drug washout periods*
- *If drugs or biologics are being administered provide information on dosing and route of administration*
- *Clearly indicate which procedures are only being conducted for research purposes.*
- *If any specimens will be used for this research, explain whether they are being collected specifically for research purposes.*
- *Describe any source records that will be used to collect data about subjects*
- *Indicate the data to be collected, including long term follow-up*

[figure not shown]
We will identify potentially eligible care partners by pre-screening the EHR and conducting a chart review. Using a previously developed EHR identification tool described in Section 5, a data analyst will generate a list of potentially-eligible patients and provide a link to the data file via a PHI-secured SharePoint site. A consenting coordinator will review these patient records to confirm potential eligibility using the inclusion and exclusion criteria described in Section 7. The consenting coordinator will contact the care partner, offer a study description, confirm interest in participation, evaluate care partner and patient eligibility, review the verbal HIPAA authorization and consent information and collect verbal consent from the care partner (for themselves and surrogate consent on behalf of the individual for whom they provide care). The consenting coordinator will then send the participant via text-message a link to a REDCap survey to document consent and authorization, and complete the Time Point 1 (baseline) measures. If the care partner prefers, Time Point 1 will occur virtually with the care partner using Microsoft Teams or Zoom. The consenting coordinator will reiterate the purpose of the research and answer any questions.

We will randomize (blind allocation) the care partner to either the enhanced condition (usual care, including speech language pathologist (SLP) contact information) or the intervention (usual care, including SLP contact information, + WeCareToFeedDysphagia). The study team will collect in the Time Point 1 measures, sociodemographic information, caregiving measures, as well as baseline

ZBI-22, CarerQol, CARES Part A and Part B, EdFED-Q, and QUALID via REDCap. In addition, the study team will collect relevant clinical data from the patient record (see Section 14 for a full list of variables collected via EHR and care partner survey).

Enhanced Control Condition (n=40)

In the enhanced control condition, following completion of baseline measures, the care partner will continue to receive usual care from the patient's medical team. The study team will provide information regarding contacting a speech language pathologist for further information regarding caring for someone with AD/ABRD and OD. The care partners will also receive information regarding contact for remaining study assessments (1 month and 3 months post-discharge).

Intervention Condition (N=40)

In the intervention condition, following completion of baseline measures, the care partner will continue to receive usual care from the patient's medical team, plus the study team will provide access to WeCareToFeedDysphagia. The study team will provide all participants a copy of the information sheet, the team's contact information, and a reminder that study personnel will contact them by phone 1 week post-discharge to assess tool use and answer any questions. The study team will provide unique

usernames and passwords to participants in the intervention condition and instructions on how to access WeCareToFeedDysphagia from any smart device (e.g., smartphone) or computer. Care partners will receive a text message reminder about the WeCareToFeedDysphagia resource 1 week, 2 weeks, and 3 weeks after initial access is granted to the care giver.

Participants in both the enhanced control condition and the intervention condition will receive text message link to complete repeat assessments of the ZBI-22, CarerQol, CARES Part A and Part B, EdFED-Q, and QUALID one month post-hospital discharge (Time Point 2) and 3 months post-hospital discharge (Time Point 3) via REDCap. For those care partners who are unable to complete the REDCap survey on their own, a member of the study team will set up a 30-minute

virtual (Microsoft Teams or Zoom) call to facilitate completion of the outcome assessments.

The study team will also collect patient-centered outcomes (defined in Section 14 below) at 1-month and 3-months post initial hospital discharge.

After care partners complete their Time Point 3 assessment, we will offer all care partners access to WeCareToFeedDysphagia. |

12. STATISTICAL ANALYSIS

- *Describe how your data will be used to test the hypotheses.*
- *State clearly what variables will be tested and what statistical tests will be used.*
- *Include sample size calculations.*
- *If this is a pilot study, state which variables will be examined for hypothesis generation in later studies.*

Go/No-Go for Future Large-Scale RCT

We define the feasibility of conducting a full-scale effectiveness trial as:

- ≥40% of eligible care partners will be consented, calculated as care partners consented over those eligible and approached
- Attrition rate will be ≤30% at Time Point 3 (care partner burden at 3 months), calculated as non-completers of the assessments over consenters
- ≥80% of care partners will successfully receive the text message after enrollment, verified at the 1-week call with the research team;
- ≥90% of care partners will receive all follow-up text messages (1, 2, and 3 weeks), calculated via confirmation response in REDCap;
- ≥60% of care partners will access WeCareToFeedDysphagia (defined as reaching the home page), calculated using Google Analytics data or confirmation response in REDCap; and
- ≥45% of care partners will engage (defined as viewing ≥ 2 pages) with WeCareToFeedDysphagia, calculated using Google Analytics data or confirmation response in REDCap

We will not proceed with the full-scale RCT to determine the effectiveness of WeCareToFeedDysphagia to reduce care partner burden if we do not meet at least 3 out of the 6 criteria outlined above.

Primary, Secondary, and Exploratory Outcomes

Although the effect size is not considered a go/no go criterion, this study is designed to support a pilot RCT that will inform the sample size calculations for the full-scale effectiveness trial. **We will obtain estimates of the ES on our primary outcome (care-partner burden at 3-months post-hospital discharge) among the 2 conditions.** We will summarize variables using descriptive statistics by study condition. Specifically, we will use mean and standard deviation for

continuous variables, and frequency and proportion for categorical variables. Our primary analysis will be to compute the ES between each pair of means on the measure of burden (our primary outcome) at the 3-month assessment. For example, we will compute the ES for Condition 1 versus Condition 2 as $(\text{Mean 1} - \text{Mean 2}) / \text{Standard Deviation}$. The ES will inform our sample size and power considerations for the future full-scale RCT.

Secondary Outcomes:

- Care partner burden at 1 month post-discharge
- Care-Related Quality of Life (CarerQoL) at 1 month and 3 months post-discharge
- Percent tool engagement (Go/No-Go)
- Percent consented (Go/No-Go)
- Percent attrition at 1 month and 3 months post-discharge (Go/No-Go)

Exploratory Outcomes:

- Mediating measures:
 - CARES Part A at 1 month and 3 months post-discharge (mediating measures)
 - CARES Part B at 1 month and 3 months post-discharge (mediating measures)
 - Sociodemographics
 - Clinical data
 - Caregiving measures
- EdFED-Q at 1 month and 3 months post-discharge
- QUALID at 1 month and 3 months post-discharge
- Patient-centered outcomes at 1-month and 3 months post-discharge

Sample Size Considerations

Because this study is designed to inform the sample size calculations for a future full-scale efficacy RCT, we plan to enroll 10% of the projected sample size needed for the full-scale RCT ($N=60$ or 10% of 602, see Figure 2 and power calculation). To account for an attrition rate of 25% (based on patient mortality and care partner loss to follow-up) at 3 months, a total of $N=80$ or $n=40$ in each condition (enhanced control and intervention) is needed for the pilot RCT (increase from $N=60$ to $N=80$ based on 60×1.33 -attrition calculation). To meet our 6-month recruitment goal of $N=80$, we will need to recruit ~4 care partners per week. Based on our preliminary work demonstrating an average of ~11 eligible care partners/week, we should have no issues reaching recruitment goals for this study.

Blind Allocation Procedures

Randomized allocation will be pre-generated via code and uploaded to a REDCap file accessible only to members of the Institute of Health System Science data team. The consenting coordinator will email a member of the data team for the next allocation prior to each individual consent.

--

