8. NUMBER OF SUBJECTS

- *Indicate the total number of subjects to be accrued locally. If applicable, distinguish between the number of subjects who are expected to be pre-screened, enrolled (consent obtained), randomized and complete the research procedures.*
- *If your study includes different cohorts, include the total number of subjects in each cohort.*
- *If this is multisite study, include total number of subjects across all sites.*

The study expects to screen up to 350 potential care partners for eligibility to enroll N=80 care partners into the study. Of the N=80 participants enrolled, N=40 will be randomized (blind allocation) to an enhanced control condition (usual care, with speech language pathologist [SLP] contact information) and the remaining N=40 will be randomized to the intervention condition (usual care, with SLP contact information + WeCareToFeedDysphagia). We anticipate at least N=60 (25% attrition) participants will complete research procedures.

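### The primary effect size uses only care partners with a 3-month burden score, with no missing-data method, although 25% attrition is expected

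*Combined protocol and SAP*

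**What the plan says.** All references are to the combined protocol and SAP.

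- **Primary analysis (section 12).** The effect size on burden at 3 months is illustrated as one arm's mean minus the other's, over a standard deviation. No analysis set, missing-data method, baseline adjustment, dropout sensitivity analysis or confidence interval is given. The result is to feed the sample size of the full-scale RCT.
- **Expected loss.** Section 12 sets the pilot size "To account for an attrition rate of 25% (based on patient mortality and care partner loss to follow-up) at 3 months". Section 8 agrees: "We anticipate at least N=60 (25% attrition) participants will complete research procedures".
- **Retention criterion (section 12).** "Attrition rate will be ≤30% at Time Point 3 (care partner burden at 3 months), calculated as non-completers of the assessments over consenters". It sets no limit for either arm or for the difference between arms. It is one of six criteria, and the full-scale trial is ruled out only "if we do not meet at least 3 out of the 6 criteria outlined above".
- **Data available.** Sections 11 and 14 collect the ZBI-22 at baseline, 1 month and 3 months. Section 16 keeps data gathered before a withdrawal but does not say how they enter the 3-month effect size.
- **Contact by arm (section 11).** Under the intervention condition there are tool reminders at 1, 2 and 3 weeks, and a notice that "study personnel will contact them by phone 1 week post-discharge to assess tool use and answer any questions". The control paragraph mentions "information regarding contact for remaining study assessments (1 month and 3 months post-discharge".

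**The concern.** A mean of 3-month scores describes the people who supplied one. The plan names two reasons for missing scores, death of the patient and loss of the care partner, and either could be related to burden. If the missing care partners differ in burden from those who remain, and the pattern differs by arm, the difference in observed means is not the difference between the arms as randomised.

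The effect size is not a go/no-go criterion, but it is the primary result and the stated input to full-scale planning. An upward bias would make the next trial too small. The baseline and 1-month ZBI-22 scores could recover some of the lost information and are already collected, but the primary formula has no place for them. The attrition criterion responds only to the total lost, not to how the loss divides between arms.

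**Working it through.** **1. The plan's own sample size.** Inputs from section 12: 602 for the full-scale trial, a 10% pilot, 25% attrition.

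- 10% × 602 = 60.2, taken as 60.
- 60 / 0.75 = 80. The plan's route, 60 × 1.33 = 79.8, also rounds to 80.

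The 80 reproduces. The 602 cannot be checked, because its alpha, power and effect size are not in the readable text ("10% of 602, see Figure 2 and power calculation"; the figure is not shown).

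**2. What the pooled criterion lets through.** The limit is 0.30 × 80 = 24 non-completers over two arms of 40. These splits all total 24/80 = 30% and pass:

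| Non-completers | Attrition by arm | Fisher exact p |
|---|---|---|
| 12 and 12 | 30% and 30% | 1.00 |
| 8 and 16 | 20% and 40% | 0.087 |
| 6 and 18 | 15% and 45% | 0.007 |

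At the planned 25% (20 non-completers), 5 and 15 (12.5% and 37.5%, p = 0.019) passes too.

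**3. Bias in the difference of observed means.** Let *d* be an arm's attrition. Let *g* be the amount, in SD units, by which non-completers' 3-month burden exceeds completers', taken as equal in both arms. The full-arm mean equals the completer mean + *d* × *g*, so

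bias = −(*d* intervention − *d* control) × *g*.

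The documents give no value for *g*; 0.25 to 1.0 is an assumed range.

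| Attrition gap | *g* = 0.25 | *g* = 0.5 | *g* = 1.0 |
|---|---|---|---|
| 0 points | 0 | 0 | 0 |
| 20 points | 0.05 | 0.10 | 0.20 |
| 30 points | 0.075 | 0.15 | 0.30 |

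The direction depends on which arm loses more and on the sign of *g*. If the intervention arm loses more and its non-completers are the more burdened, the bias favours the intervention.

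**4. Scale for the next trial.** Assume 602 is the analysed total at two-sided 5% and 80% power. The implied effect is (1.960 + 0.842) × √(2/301) = 0.228 SD. At 90% power, or if 602 already includes 25% dropout, or both, it is 0.26 to 0.31 SD. Starting from 0.228:

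- Upward bias 0.05 (0.278): 203 per arm instead of 301; power at the true 0.228 about 63%.
- Upward bias 0.10 (0.328): 146 per arm; power about 50%.

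**5. Random error.** With 30 completers per arm the 95% half-width is 1.96 × √(2/30) = 0.51 SD; with 28 per arm it is 0.52 SD.

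**6. Would a 30% limit in each arm be a cheap repair?** Take true attrition as the plan's 25% in both arms.

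- Pooled rule fails: P(X ≥ 25 of 80) = 0.12.
- One arm passes: P(X ≤ 12 of 40) = 0.82. Both pass: 0.82² = 0.67. The per-arm rule therefore fails with probability 0.33.

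**The case against.** A reader might infer four stronger points. The documents do not support them.

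- **That unequal dropout would go unseen.** Section 12 promises descriptive summaries by arm and lists percent attrition at 1 and 3 months as a secondary outcome. A per-arm table is the natural reading. It is not explicitly promised, however, and nothing follows from it.
- **That unequal dropout is likely.** The tool reminders belong to the intervention arm, but the sentence announcing the 1-week call opens by addressing all participants, so its scope is unclear. Assessment links, help with completion and payments are the same in both arms, and controls are offered the tool after the 3-month assessment. Unequal dropout is plausible, no more. With equal true attrition of 25%, a gap of 12 or more people has a probability of about 0.003. The 6 and 18 split shows what the rule allows; it is not a forecast.
- **That the plan prescribes a completers-only analysis.** This is inferred from the formula, which is introduced as an example, and from silence on missing data.
- **That the go decision turns on this.** Three of six criteria suffice, and the effect size is not one of them.

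It is also fair that random error of about ±0.51 SD exceeds the biases in the table. That limits the practical weight of the point but does not remove it, because a confidence interval does not reveal bias, and none is planned. Nor is a mixed model a full cure. It relies on data missing at random, and it implicitly predicts caregiving burden for people whose patient has died.

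**Conclusion.** The concern holds in a limited form. As written, the primary estimate rests on observed 3-month scores alone, with no missing-data method, in a study that plans for a quarter of participants not completing. A better estimator is available from data already scheduled.

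The size is conditional: 0.05 to 0.20 SD for a 20-point attrition gap, if non-completers differ by an assumed 0.25 to 1.0 SD. It is zero if missingness is unrelated to burden. In this calculation it is also zero when attrition is equal, but equal attrition for different reasons in the two arms could still bias the estimate. The bias should not be quoted as a fixed share of the full-scale effect, because the 0.228 SD benchmark depends on an assumed alpha and power.

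The pooled criterion cannot flag the problem, but that is a reason to report attrition by arm, not to add a second threshold. A 30% limit in each arm would raise the chance of failing from about 12% to about 33% with no true difference in dropout.

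**What to change.** In section 12:

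1. Estimate the 3-month difference from a mixed model for repeated measures on all randomised care partners, using baseline, 1-month and 3-month ZBI-22. Divide it by the raw ZBI-22 SD, not a residual SD from the model, so that it stays on the scale used for sample size. Report it with a 95% confidence interval.
2. State how burden after the patient's death is treated, so that the estimate has a defined meaning for those care partners.
3. Add a sensitivity analysis for informative dropout, for example by shifting the unobserved 3-month scores over a stated range, separately by arm.
4. Report attrition at 1 and 3 months by arm and reason, with patient death separate from loss to follow-up.
5. Leave the pooled 30% go criterion as it is, and do not add a per-arm 30% threshold.

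The sample size stays at 80 and no new outcome measurement is needed. The cost is revised SAP wording, a recorded reason for each non-completion and a little more analysis work.

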14. DATA MANAGEMENT AND CONFIDENTIALITY

- *Describe the data and specimens to be sent out or received. As applicable, describe:*
 - *What information will be included in that data or associated with the specimens?*
 - *Where and how data and specimens will be stored?*
 - *How long the data will be stored?*
 - *Who will have access to the data?*
 - *Who is responsible for receipt or transmission of data and specimens?*
- *Describe the steps that will be taken to secure the data during storage, use and transmission.*

Regular meetings will take place with the PI and other members of the study team to ensure protocol adherence and data accuracy. This protocol collects data from electronic health records (EHR) and self-reported surveys.

Both EHR and survey data will be collected and stored securely in coded format within REDCap, a Northwell-approved system for collecting and storing research data, including PHI. Only IRB-approved members of the study team will have access to the study REDCap.

Data Variables To-Be Collected:

Care Partner Burden

Post-hospital care partner burden will be assessed using the Zarit Burden Scale (ZBI-22) at 3 months. The ZBI-22 addresses personal strain, which is rated with 5 frequency-related response categories, scored 0 (never) to 4 (nearly always). The total score ranges between 0 and 88 (higher scores indicating higher burden). A score less than 21 has been suggested to indicate care-partner burden. We will measure care-partner burden at baseline, 1 month, and 3 months (long term) using technology. Outcome

measures will be captured through a REDCap link which will be sent to the care partner's smart phone/device.

Care-Related Quality of Life (CarerQol)

Post-Hospital Care-Partner Quality of Life will be measured using the Care-Related Qol-7D. The Care-Related Qol-7D measures well-being (CarerQol-VAS or visual analog scale) and subjective burden (CarerQol-7D). The CarerQol-VAS measures happiness, using endpoints between 'completely unhappy' (0) and 'completely happy' (10). Subjective burden is measured on 7 dimensions (fulfillment, relational problems, mental health, daily activities problems, physical health, and support), and rated as (i) no, (ii) some, and (iii) a lot. The weighted score ranges from 0-100 (worst to best caregiving situation). We will measure care-partner quality of life using technology. Outcome measures will be captured through a REDCap link which will be sent to the care partner's smart phone/device.

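### The primary effect size compares raw 3-month ZBI-22 means and makes no use of the baseline ZBI-22 the trial collects, giving up precision at no saving

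*Combined protocol and SAP*

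**What the plan says.** Section 12 (Primary, Secondary, and Exploratory Outcomes) sets the target: "We will obtain estimates of the ES on our primary outcome (care-partner burden at 3-months post-hospital discharge) among the 2 conditions". It then names the estimator: "Our primary analysis will be to compute the ES between each pair of means on the measure of burden (our primary outcome", with burden taken at Time Point 3. The formula follows: "For example, we will compute the ES for Condition 1 versus Condition 2 as" the difference between the two condition means over a standard deviation. Which standard deviation is meant is not stated.

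The use is also stated: "The ES will inform our sample size and power considerations for the future full-scale RCT". The same section limits the consequence for the pilot itself: "Although the effect size is not considered a go/no go criterion".

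Section 14 (Care Partner Burden) confirms that the same instrument is available before treatment: "We will measure care-partner burden at baseline, 1 month, and 3 months (long term) using technology". Section 11 lists ZBI-22 among the Time Point 1 measures and places tool access after those measures are complete. Section 12 mentions no ANCOVA, change score, repeated-measures model or covariate list. Sociodemographic, clinical and caregiving variables appear only under exploratory mediating measures. No stratification on baseline burden is described.

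**The concern.** In a small trial with a repeated continuous scale, part of the variation in the 3-month score can usually be explained by the same person's score at entry. An estimator that ignores the entry score leaves that variation in the treatment contrast. Any chance difference in baseline burden between the arms then carries into the effect size, in proportion to the baseline-to-3-month correlation.

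The effect size is the declared primary analysis, and its stated purpose is to help size the full-scale RCT. Its precision therefore matters more than that of a descriptive by-product. If the later trial adjusts for baseline, its sample size also needs the baseline-to-3-month correlation, which Section 12 does not plan to report.

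**Working it through.** **The plan's own size.** Section 12 takes 10% of 602: 0.10 × 602 = 60.2, about 60. Allowing for 25% attrition, 60 / 0.75 = 80 (the plan's 60 × 1.33 = 79.8), or 40 per arm. The 80 reproduces. Section 8 agrees on completers: "We anticipate at least N=60 (25% attrition) participants will complete research procedures", which is 30 per arm. The 602 cannot be checked, because its alpha, power and effect are not in the available text and Figure 2 is not shown.

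**Raw estimator.** For a small effect, SE = sqrt(2/n) in SD units. With n = 30, SE = sqrt(2/30) = 0.258, and the 95% half-width is 1.96 × 0.258 = 0.51. Including the effect-size term, sqrt(2/n + d²/(4n)), at d = 0.25 gives 0.259 and again 0.51.

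**Baseline-adjusted estimator.** SE = sqrt(2/n) × sqrt(1 − r²), where r is the baseline-to-3-month correlation of ZBI-22. The values of r are assumptions. The equivalent number of raw completers per arm is 30 / (1 − r²).

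| r (assumed) | sqrt(1 − r²) | SE | Half-width | Narrower by | Equivalent per arm |
|---|---|---|---|---|---|
| 0.3 | 0.954 | 0.246 | 0.48 | 5% | 33 |
| 0.5 | 0.866 | 0.224 | 0.44 | 13% | 40 |
| 0.6 | 0.800 | 0.207 | 0.40 | 20% | 47 |
| 0.7 | 0.714 | 0.184 | 0.36 | 29% | 59 |

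Allowing for the degree of freedom spent on the covariate adds less than 0.005 to each half-width.

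**Simulation check.** This used 30 per arm, true effect 0.25, 20,000 runs, and both estimates divided by the pooled 3-month SD. The SD of the estimate, raw against adjusted, was 0.265 against 0.255 at r = 0.3, 0.264 against 0.230 at 0.5, and 0.261 against 0.190 at 0.7. Both estimators averaged about 0.25, so neither is biased.

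**Chance imbalance.** The raw variance splits as 2/n = (2/n)r² + (2/n)(1 − r²). The first part is the contribution of baseline imbalance; adjustment removes it. At r = 0.6 this is 0.0667 = 0.0240 + 0.0427. The imbalance contribution therefore has SD sqrt(0.0240) = 0.155 and median absolute value 0.6745 × 0.155 = 0.10. It is already inside the 0.51 half-width.

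**Scale.** The effect detectable with total N is sqrt(2/(N/2)) × (z for alpha + z for power). Two-sided alpha 0.05 is assumed.
- 602 analysed: 0.23 at 80% power, 0.26 at 90%.
- 602 × 0.75 = 451.5 analysed: 0.26 at 80% power, 0.31 at 90%.

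**The case against.** The strongest reply is that the raw comparison is a legitimate estimator. Randomisation makes it unbiased, no hypothesis test hangs on it, and the effect size does not enter the go/no-go decision. All of that stands. This is a matter of efficiency, not validity.

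The size of the gain is also open. Baseline is taken around a hospital stay and the endpoint falls 3 months after discharge, so a low correlation is plausible. At 0.3 the interval narrows by only about 5%.

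Four stronger readings are tempting, and the documents do not support them.

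- A reader might infer that the raw effect size is biased. Chance imbalance affects the one realised trial but is not systematic.
- A reader might count imbalance as a second harm on top of imprecision. It is one component of the same variance.
- A reader might set the 0.155 against an effect of 0.23 and conclude that imbalance typically amounts to two-thirds of the target. But 0.155 is one standard deviation at one assumed correlation, the median absolute contribution is about 0.10, and 0.23 is only the lower end of a range that rests on assumed alpha, power and attrition.
- A reader might infer that the correlation is lost. It can be computed from data already planned; Section 12 simply does not commit to reporting it. Nor do the documents available say that the full-scale RCT will use ANCOVA.

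None of this gives a reason to leave baseline ZBI-22 out of the estimate.

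**Conclusion.** The point holds as a worthwhile improvement to the declared primary analysis. At 30 completers per arm, adjustment would reduce the 95% half-width from about 0.51 SD to between 0.48 and 0.36 SD for correlations of 0.3 to 0.7. The gain is slight at the low end and material from about 0.5 upwards. The figures assume equal arms, a common SD and a linear relation between baseline and 3-month scores.

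It would be wrong to conclude that adjustment makes the pilot effect size fit for sizing the next trial. Even 0.36 exceeds the whole 0.23 to 0.31 range of effects that 602 would correspond to under the assumptions above.

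**What to change.** In Section 12, before outcomes are analysed:

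1. Make the primary estimate the between-condition difference in 3-month ZBI-22 from an ANCOVA with baseline ZBI-22 as covariate, reported with its 95% CI.
2. Name the SD used to standardise it. The pooled 3-month SD fits the stated purpose of sizing a 3-month endpoint; the pooled baseline SD is acceptable if justified. The residual SD is not, because it would inflate the effect size.
3. Report the baseline and 3-month SDs and the baseline-to-3-month correlation, so that a later sample size can use the (1 − r²) factor if it adjusts for baseline.
4. Keep the raw effect size as a descriptive figure.
5. State a rule for missing baseline items, since Section 17 lets participants skip questions.
6. Say that the interval will remain wide and that the point estimate alone should not set the full-scale sample size.

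A change score is not an equal substitute. Its variance relative to the raw analysis is 2(1 − r), which is 1.4 at r = 0.3 and only breaks even at 0.5.

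The cost is a few sentences of wording and one regression, with no new data collection.
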